6.9. Compliance

Based on the FAS, analyze and tabulate the compliance of the subjects. For subjects who were randomized but did not receive any investigational product, or who were randomized but received different dose groups, the compliance will be 0. Summarize descriptively the continuous and categorical (<80%, 80% - 120%, >120%) outcomes for the following indicators: total cumulative number of drugs dispensed (capsules), total cumulative number of drugs recovered (capsules), total cumulative number of drugs lost/damaged (capsules), actual cumulative number of drugs administered (capsules), planned duration of drug administration (days), planned cumulative number of drugs administered (capsules), and medication compliance (%). For specific definitions and calculation methods, please refer to Section [6.2.2.](#)

6.10. Efficacy Analysis

The primary efficacy endpoint analysis will be conducted based on both the FAS and PPS, while the secondary efficacy endpoint analysis will be performed based on the FAS.

Descriptive statistics will be performed for changes from baseline in MDS-UPDRS part scores and total scores at each visit.

6.10.1. Primary Efficacy Endpoint Analysis

The primary efficacy endpoint of this study is the change from baseline in the Movement Disorder Society-Unified Parkinson's Disease Rating Scale (MDS-UPDRS) Part III (Motor Examination) score after 12 weeks of treatment. Evaluation time point: ≥ 12 hours from the most recent dose of anti-PD drug. The statistical methods, strategies for concomitant events, and handling of missing values are summarized in the following table:

Analysis	Analysis Population	Statistical Analysis Methods	Strategies and Missing Data Handling
Primary Analysis	FAS	Mixed Model for Repeated Measures (MMRM)	Treatment strategy, no imputation for missing values
Sensitivity Analysis 1	FAS	Analysis of Covariance (ANCOVA)	Treatment strategy, LOCF for missing value imputation
Sensitivity Analysis 2	FAS	Mixed Model for Repeated Measures (MMRM)	Treatment strategy, MI for missing value imputation
Supplementary Analysis 1	PPS	Mixed Model for Repeated Measures (MMRM)	Treatment strategy, no imputation for missing values
Supplementary Analysis 2	FAS	Mixed Model for Repeated Measures (MMRM)	A hypothetical strategy of employing MI to impute missing data.

6.10.1.1. Primary Analysis

The analysis will be performed using a mixed models for repeated measures (MMRM) with the changes from baseline in the MDS-UPDRS Part III scores after 12 weeks of treatment as the dependent variable, whether subjects have been receiving levodopa, the background medication for PD (yes vs. no) at a stable dose at baseline and the baseline MDS-UPDRS Part III score as the covariates, and the treatment group, visit, and the treatment group-by-visit interaction as the fixed effects. The covariance matrix prioritizes an unstructured (UN) covariance matrix. If the results do not converge, the following covariance structures will be tested sequentially: heterogeneous Toeplitz (TOEP), first-order autoregressive (AR1), and compound symmetry (CS). The first covariance structure that achieves convergence will be used. Based on the model, calculate the least squares mean of the change from baseline in MDS-UPDRS Part III score at 12 weeks of treatment, along with its 95% CI, the between-group difference in least squares means with its two-sided 95% CI, and the nominal P-value.

6.10.1.2. Sensitivity Analysis Methods

The sensitivity analysis of the primary endpoint will be conducted based on the FAS.

Sensitivity Analysis 1: For missing data in the primary endpoint, a Last Observation Carried Forward (LOCF) imputation will be applied, followed by a sensitivity analysis using Analysis of Covariance (ANCOVA). The imputation rules are detailed in Section [6.2.1](#). The model used the change from

baseline in the MDS-UPDRS Part III score at 12 weeks of treatment as the dependent variable, with baseline stable use of levodopa as anti-PD background medication (yes vs. no), baseline MDS-UPDRS Part III score, and treatment group as covariates. Based on the model, calculate the least squares mean of the change from baseline in MDS-UPDRS Part III score at 12 weeks of treatment, along with its 95% CI, the between-group difference in least squares means with its two-sided 95% CI, and the nominal P-value. The reference procedure is as follows:

```
ODS OUTPUT lsmeanc1=lsmeans lsmeandiffcl=lsmeansdiff;
```

```
PROC GLM data=dataset;
```

```
  CLASS trtpn pd;
```

```
  MODEL chg = trtpn pd base/SOLUTION;
```

```
  LSMEANS trtpn/CL STDERR PDIFF COV;
```

```
run;
```

Sensitivity Analysis 2: Assuming the missing data mechanism is missing at random (MAR), a sensitivity analysis will be conducted using the same method as the primary analysis after performing multiple imputation for missing values. For imputation rules, refer to Section [11.1](#) of the SAP Appendix.

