#### **11.4.3 Sensitivity Analysis**

The sensitivity analysis of the primary endpoint will be performed using the analysis of covariance. The model will use the changes from baseline in the MDS-UPDRS Part III scores after 12 weeks of treatment as the dependent variable, whether subjects have been receiving levodopa, the background medication for PD (yes vs. no) at a stable dose at baseline, the baseline MDS-UPDRS Part III score, and the treatment group as the covariates.

After the primary endpoint is imputed by using different mechanisms for imputing the missing data, the sensitivity analysis will be performed using the same method as that for the primary analysis. Detailed statistical methods will be described in a separate SAP.

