6.2. Data Handling Methods

6.2.1. Missing Data

Missing Data Handling

1) Multiple Imputation (MI) Method

The MI method will be applied for the sensitivity analysis of the primary endpoint. For all subjects in the FAS, missing data of the primary endpoint—the score of Part III (Motor Examination) of the Movement Disorder Society-Unified Parkinson's Disease Rating Scale (MDS-UPDRS) at 12 weeks post-dose (evaluation time point: ≥ 12 hours after the last dose of anti-PD drug)—will be imputed. The imputation rules are detailed in Section [11.1](#) of the Appendix in SAP.

2) Last Observation Carried Forward (LOCF) Method

The LOCF method will be applied for sensitivity analysis of the primary endpoint. For all subjects in the FAS, missing data of the primary endpoint—the score of Part III (Motor Examination) of the Movement Disorder Society-Unified Parkinson's Disease Rating Scale (MDS-UPDRS) at Week 12 (assessment time point: ≥ 12 hours after the last dose of anti-PD drug)—will be imputed. Missing data will be imputed using the last non-missing observation prior to the visit after baseline (excluding baseline).

3) Missing Date:

For incomplete date data, the dates in the list will be presented according to the actual circumstances. The missing date imputation rules are as follows:

Missing AE Onset Date

- Only day missing: If the year and month of the AE onset date are the same as the year and month

of the first dose date, and the AE end date is confirmed to be no earlier than the first dose date or missing, then the first dose date will be used as the AE onset date. Otherwise, impute as the 1st day of the month.

- Month and day missing: If the year of the AE onset date is the same as the year of the first dose date, and the AE end date is confirmed to be no earlier than the first dose date or missing, then the first dose date will be used as the AE onset date. Otherwise, impute as January 1 of that year;
- Year, month, and day missing: Impute with the subject's first dose date.

Missing AE End Date

- Only day missing: impute as the date of the last day of the month;
- Month and day missing: imputed as December 31 of that year;
- Year, month, and day missing: no imputation.

The imputation of the end date should not be earlier than the onset date.

Missing Or Incomplete Start Dates Of Previous And Concomitant Medications/Non-Drug Therapies

- Only day missing: impute as the first day of the month;

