6.10.1.3. Supplementary Analysis Methods

Supplemental Analysis 1: Based on PPS, summarize using the same statistical methods described in the primary analysis in Section [6.10.1.1](#).

Supplementary Analysis 2: Based on the FAS, summarize concomitant events using the hypothetical strategy with the same statistical methods described in Section [6.10.1.1](#) for the primary analysis.

Concomitant Events and Handling Strategy: Any concomitant medications (excluding the investigational product and stable anti-PD medications at the time of enrollment) or treatments that may impact the PD progression will be addressed using the hypothetical strategy, wherein data following the concomitant event will be excluded and treated as missing data. Assuming the missing mechanism is missing at random (MAR), multiple imputation will be performed for missing values prior to analysis. For imputation rules, refer to Section [11.1](#) of the SAP Appendix.

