11.1. Appendix A Multiple Imputation (MI) Method

MI will adhere to the following steps:

Step 1: For non-monotone missing data, assuming the missing mechanism is missing at random (MAR), the MCMC method will be used with 100 iterations for imputation. The corresponding SAS option will be MCMC IMPUTE = MONOTONE. The number of imputed seeds will be set to 12345. The upper and lower bounds of the MDS-UPDRS Part III (Motor Examination) score will be [0, 132], with imputed scores rounded to the nearest integer. If applicable, covariates include whether stable levodopa-based anti-PD medication was received at screening (yes vs. no), baseline values (base), and scores at post-baseline visits (weeks 1, 4, 8, and 12 of treatment). The order in which these variables enter the procedure step follows the sequence listed above. The imputed data constitutes monotone missing data, and these 100 datasets will be utilized in Step 2. The reference program for the SAS PROC MI procedure is as follows:

```
PROC MI DATA=adeff NIMPUTE=100 OUT=mi_monotone SEED=12345
```

```
ROUND=.. 1 1 1 1
```

```
MIN =.. 0 0 0 0
```

```
MAX =.. 132 132 132 132;
```

```
MCMC IMPUTE=MONOTONE;
```

```
VAR pd base week1 week4 week8 week12;
```

```
RUN;
```

Step 2: For the monotone missing data imputed in Step 1, assuming the missing mechanism is MAR, use the MONOTONE REG method for imputation. The corresponding SAS PROC MI option is MONOTONE REG. The missing values at post-baseline visits will be imputed using the results from the immediately preceding visit. The seed number for imputation will be set to 23456. The reference program for the SAS PROC MI procedure is as follows:

```
PROC MI DATA=mi_monotone NIMPUTE=1 OUT=mi_complete SEED=23456
```

```
ROUND=.. 1 1 1 1
```

```
MIN =.. 0 0 0 0
```

```
MAX =.. 132 132 132 132;
```

```
MINMAXITER=1000;
```

```
BY _imputation_;
```

```
CLASS pd;
```

```
VAR pd base week1 week4 week8 week12;
```

```
MONOTONE REG(pd base week1 week4 week8 week12);
```

```
RUN;
```

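### No planned analysis of the primary endpoint varies the assumption about unobserved Week 12 scores, so none can show how far informative dropout could move the result

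*SAP*

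**What the plan says.** SAP 6.10.1 tabulates five analyses of the change in MDS-UPDRS Part III at Week 12.

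- **Primary:** MMRM on the FAS, described as "Treatment strategy, no imputation for missing values".
- **Sensitivity Analysis 1 (6.10.1.2):** LOCF followed by ANCOVA. Under 6.2.1 the last post-baseline score is carried to Week 12; baseline is never carried.
- **Sensitivity Analysis 2 (6.10.1.2):** multiple imputation, then the primary model: "Assuming the missing data mechanism is missing at random (MAR), a sensitivity analysis will be conducted using the same method as the primary analysis".
- **Supplementary Analysis 1 (6.10.1.3):** the same MMRM on the PPS.
- **Supplementary Analysis 2 (6.10.1.3):** scores after other PD therapy are set to missing, and then "Assuming the missing mechanism is missing at random (MAR), multiple imputation will be performed for missing values prior to analysis".

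Both imputed analyses use SAP Appendix A (11.1), where both steps are MAR. For the second step: "assuming the missing mechanism is MAR, use the MONOTONE REG method for imputation". Its regression statement begins "MONOTONE REG(pd base week1 week4 week8 week12", which holds the levodopa stratum, baseline and the visit scores, with no term for randomised arm.

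Protocol 11.4.3 asks for sensitivity analyses with the endpoint "imputed by using different mechanisms for imputing the missing data" and leaves the detail to the SAP. Neither document contains a delta-adjusted, tipping-point or reference-based analysis.

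**The concern.** Missing Week 12 scores may well be related to how patients are doing. Protocol 4.4 provides for withdrawal after hepatic events, intolerable adverse events or poor compliance. Protocol 7.2.2 lets the investigator withdraw a patient who has used a prohibited therapy. Protocol 5.3.2.3 ends treatment after emergency unblinding, and 4.4 lists unblinding among the withdrawal conditions. Under 5.4 an individual's study ends at early withdrawal. Such patients have an early withdrawal visit, but the SAP's analysis visits (6.1) are baseline and V3 to V6 only, and the withdrawal visit is not mapped to any of them.

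Whether those who leave would have scored like those who stay, given their earlier scores, cannot be tested from the data. A sensitivity analysis should show how far that assumption must fail before the conclusion changes, and the planned set does not do this. The stake is the interpretation of the treatment difference that this phase II trial carries forward.

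**Working it through.** **1. What each analysis assumes about an unobserved Week 12 score**

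| Analysis | Assumption | Can it be varied? |
|---|---|---|
| Primary MMRM | MAR given arm, visit, stratum, baseline and earlier scores (implied by the method; the SAP does not state it) | No |
| Sensitivity 1 | Score stays at the last post-baseline value; single imputation | No |
| Sensitivity 2 | MAR given stratum, baseline and earlier scores, without arm | No |
| Supplementary 1 | As primary, on the PPS | No |
| Supplementary 2 | As Sensitivity 2, with more scores set to missing | No |

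**2. Size of the hidden error**

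The documents state no dropout rate, SD or effect size (Protocol 11.1, SAP 4), so there is no figure of theirs to reproduce. The arm size is theirs: 150/2 × 2/3 = 50 per active arm, and 2 × 25 = 50 on placebo.

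Suppose a fraction d of the active arm is unobserved at Week 12 and truly delta points worse than MAR predicts, with no departure on placebo. The true active mean exceeds the MAR mean by d × delta, so the MAR estimate is too favourable by that amount. With departures in both arms the error is d(active) × delta(active) − d(placebo) × delta(placebo), so equal departures cancel.

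Assumed range:

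- d = 10%, delta = 4: 0.10 × 4 = 0.4 points
- d = 15%, delta = 6: 0.15 × 6 = 0.9 points
- d = 20%, delta = 8: 0.20 × 8 = 1.6 points
- d = 25%, delta = 8: 0.25 × 8 = 2.0 points

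Approximate SE of a difference, 50 per arm: SD × √(2/50) = 0.2 × SD, which is 1.4 for SD 7 and 1.8 for SD 9 (assumed). The error therefore runs from 0.4/1.8 = 0.22 SE to 2.0/1.4 = 1.43 SE.

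**3. Do the planned estimators respond to delta?**

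A large-sample simulation (100,000 per arm, one active arm against placebo, visits at Weeks 1, 4, 8 and 12) used assumed inputs: SD 8, between-visit correlation 0.6, Week 12 effect −3, dropout 20% active and 10% placebo. The shift was applied only to active dropouts' unseen Week 12 scores. Sequential regression with arm stood in for the MMRM, and the same regression without arm for Appendix A.

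| Shift | Truth | MMRM-type | Appendix A model | LOCF ANCOVA |
|---|---|---|---|---|
| 0 | −2.99 | −2.98 | −2.65 | −2.67 |
| 3 | −2.36 | −2.97 | −2.63 | −2.65 |
| 6 | −1.83 | −3.02 | −2.68 | −2.70 |
| 10 | −0.98 | −2.99 | −2.66 | −2.69 |

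The truth moves by about 2 points and the estimators do not move beyond simulation noise. At shift 0 nothing is informative, yet the Appendix A model still differs from the MMRM-type estimate by 0.33 (2.98 − 2.65). That gap comes from leaving arm out: imputed scores are pulled towards the pooled mean. With 10% dropout in both arms and no shift the gap is 0.22 (3.04 − 2.82).

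**4. What a tipping-point analysis would add**

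For an assumed estimate of −4 with SD 8 (SE 1.6), the shift that brings the upper 95% limit to zero is (4 − 1.96 × 1.6)/d = 0.864/d: 8.6, 4.3 or 2.9 points at 10%, 20% or 30% active dropout. A clinician can judge whether such a shift is plausible. No planned analysis yields that number.

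**The case against.** The strongest reply is that the consequence is limited and its size assumed. The SAP (6.1) declares no formal hypothesis test and only nominal P-values, so type I error control is not at issue. The range in points is d × delta by construction, and all of it rests on inputs the documents do not give. Phase I reported similar adverse event incidence on drug and placebo (Protocol 2.4.2), though in healthy subjects dosed for at most 7 days. All of this stands, and it limits the point to one of interpretation.

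The reply also corrects four stronger readings that a reader might infer:

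- *Sensitivity Analysis 2 must reproduce the MMRM, so agreement is automatic.* The documents do not support this. Appendix A omits arm, so the two can differ. The complaint is that neither responds to delta.
- *Every planned analysis is at least as favourable as MAR.* LOCF is not an MAR method and was less favourable than the MMRM-type estimate in the simulation. That is incidental and uncalibrated, and its direction depends on a trajectory that neither document gives.
- *The SAP breaks a protocol commitment to a missing-not-at-random analysis.* Protocol 11.4.3 speaks of mechanisms for imputing, which LOCF and multiple imputation can satisfy.
- *Use of other PD therapy is itself missing data.* Protocol 7.2.2 allows continued follow-up, the primary analysis names a treatment strategy for such use, and Supplementary Analysis 2 takes the hypothetical view. Only withdrawal afterwards creates missing scores.

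None of this supplies an analysis in which the assumption about dropouts is varied.

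**Conclusion.** The point holds as a recommended improvement. All five planned analyses of the primary endpoint either rely on MAR or fix a single carry-forward value, and none can show how sensitive the treatment difference is to dropouts doing worse than predicted. A gap between Sensitivity Analysis 2 and the MMRM would also be hard to read, because the missing arm term produces one by itself.

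Under the assumed range the hidden error is 0.4 to 2.0 points, about 0.2 to 1.4 standard errors. This rests on assumed dropout of 10–25%, a departure of 4–8 points confined to the active arm, and SD 7–9 with 50 per arm. If dropout is low, or departures are similar in both arms, it is small. The absence of such an analysis is certain from the text; the size is not. The documents do not show that the primary estimate will be biased.

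**What to change.** Before database lock and unblinding (Protocol 5.3.2.2), amend the SAP as follows.

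1. **Appendix A:** include randomised arm in the imputation model in both steps. Supplementary Analysis 2 uses the same appendix and benefits as well.
2. **Sensitivity Analysis 2:** extend it to a delta-adjusted (tipping-point) multiple imputation. Add, for example, 0, 2, 4, 6 and 8 points to imputed Week 12 scores in the TJ0113 arms, refit the MMRM, pool by Rubin's rules, and report each dose's difference from placebo with its 95% CI at every delta. Delta = 0 is the MAR result, so nothing planned is lost. A copy-reference version, imputing dropouts from placebo, may be added.
3. **Sensitivity Analysis 1:** keep LOCF with ANCOVA as planned, but state that its agreement with the MMRM is not evidence against informative dropout.

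The cost is SAP wording and a few lines in the existing PROC MI program. The downside is a little more programming and a robustness statement that may look less favourable. The delta range should be set now, because one chosen after unblinding would carry little weight.

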6.10.1.3. Supplementary Analysis Methods

Supplemental Analysis 1: Based on PPS, summarize using the same statistical methods described in the primary analysis in Section [6.10.1.1](#).

Supplementary Analysis 2: Based on the FAS, summarize concomitant events using the hypothetical strategy with the same statistical methods described in Section [6.10.1.1](#) for the primary analysis.

Concomitant Events and Handling Strategy: Any concomitant medications (excluding the investigational product and stable anti-PD medications at the time of enrollment) or treatments that may impact the PD progression will be addressed using the hypothetical strategy, wherein data following the concomitant event will be excluded and treated as missing data. Assuming the missing mechanism is missing at random (MAR), multiple imputation will be performed for missing values prior to analysis. For imputation rules, refer to Section [11.1](#) of the SAP Appendix.

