## 5 Overall Trial Design

### 5.1 Trial Design

#### 5.1.1 Overall Design

This study is a randomized, double-blind, placebo parallel-controlled phase II clinical trial which is designed to assess the efficacy and safety of TJ0113 capsules in the treatment of patients with early-stage PD. It is planned to include approximately 150 subjects with early-stage PD who will be randomized in a 1:1 ratio into two cohorts (Cohort 1: 200 mg dose group; Cohort 2: 400 mg dose group). Within each cohort, subjects who have been successfully screened will be randomly assigned to TJ0113 capsules group and the placebo group in a ratio of 2:1 within each stratum based on a stratification factor whether they have been receiving levodopa, the background medication for PD (yes vs. no) at a stable dose. Among them, approximately 50 subjects will receive TJ0113 capsules and approximately 25 subjects will receive the placebo. In this study, there will be approximately 50 subjects in each of the TJ0113 capsules 200 mg group, TJ0113 capsules 400 mg group and the placebo group. After randomization, subjects will receive the oral administration of TJ0113 capsules or the placebo for 12 consecutive weeks and continue to receive follow-up visits for 1 week (telephone follow-up) after the end of treatment. For subjects who have been receiving the anti-PD drug at a stable dose for at least 4 weeks prior to study entry, the original regimen of the background medication for PD should be maintained during the study.

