#### 7.2.1 Permitted Concomitant Medications/Therapies

Concomitant medications/therapies allowed to be administered from signing of the ICF to 1 week after the last dose of the investigational product include:

- Background medications for PD that have been stably used for at least 4 weeks before study entry, of which the treatment regimen can remain unchanged (for subjects who have used any background medications for PD including levodopa, if any AE such as dyskinesia occur, the dose of levodopa is allowed to be reduced at the discretion of the investigator);
- Other concomitant medication or therapies that have already been used at the time of screening, of which the original drug/therapy type, dose or treatment frequency and setting should remain unchanged as much as possible;
- Drugs required to be used for treating the AEs.

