#### 7.2.2 Prohibited Concomitant Medications/Therapies

The following medications/therapies are prohibited during the period from signing the ICF until 1 week after the last dose of the investigational product:

- Any procedure/surgery that may affect the progression of PD, including but not

limited to brain surgery (such as stereotactic destruction and deep brain stimulation) or traditional Chinese medicine physiotherapy (such as acupuncture), etc.;

- Any drugs other than investigational product that may affect the progression of PD (excluding those which have been on a stable dose for PD at the time of study entry).
- Serotonin reuptake inhibitors (such as fluoxetine, paroxetine, trazodone, citalopram, escitalopram, etc.);
- Any unauthorized drugs (i.e., other investigational drugs that are currently tested in clinical trials and have not been approved for marketing).

The investigator will determine and record the use of any emergency medication, drug name, dose, route of administration, purpose of treatment, start and end date of administration.

If subjects have used any prohibited drug or non-drug therapy, it will be recorded as a protocol deviation. The investigator decides on whether the subjects will continue the follow-up or be withdrawn from the study based on the severity of the deviation and the subjects' condition

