##### **11.4.2 Analysis for Primary Endpoint**

The primary objective of this study is to assess the efficacy of TJ0113 capsules in the treatment of patients with early-stage PD. The main concern of interest is the treatment difference in terms of the changes from baseline in the MDS-UPDRS Part III (motor examination) scores after 12 weeks of treatment between the TJ0113 capsules group and the placebo group.

Definition of estimand:

- Population: patients with early-stage PD
- Endpoint: changes from baseline in scores of MDS-UPDRS Part III (motor examination) after 12 weeks of treatment. Evaluation time point:  $\geq 12$  hours from the most recent dose of anti-PD drug.
- Treatment: treatments will be randomly assigned; subject will be randomized in a 1:1 ratio to two cohorts (200 mg dose group and 400 mg dose group); and within each cohort, the subjects will be randomized in a 2:1 ratio to the TJ0113 capsules group and the placebo group.
- Concomitant event and management strategy: For any concomitant medication (excluding the investigational product and stable anti-PD medications at the time of enrollment) or treatment that could potentially impact the PD disease process, a therapeutic strategy will be employed.
- Population-level summary: differences in the least square mean of the changes from baseline in MDS-UPDRS Part III (motor examination) scores after 12 weeks of treatment between the TJ0113 capsules group and the placebo group.

The analysis will be performed using a mixed models for repeated measures (MMRM) with the changes from baseline in the MDS-UPDRS Part III scores after 12 weeks of treatment as

the dependent variable, whether subjects have been receiving levodopa, the background medication for PD (yes vs. no) at a stable dose at baseline and the baseline MDS-UPDRS Part III score as the covariates, and the treatment group, visit, and the treatment group-by-visit interaction as the fixed effects.

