3.1. Estimand

The primary estimands of this study are as follows:

- Population: Early-stage PD patients who meet the inclusion criteria (refer to Section 4.1 of the protocol) and do not meet the exclusion criteria (refer to Section 4.2 of the protocol).
- Treatment: Patients will be randomized into one of two cohorts (200 mg and 400 mg dose groups) in a 1:1 ratio. Within each cohort, patients will be further randomized in a 2:1 ratio to receive either TJ0113 capsules or placebo.
- Endpoint: Change from baseline in the Movement Disorder Society-Unified Parkinson's Disease Rating Scale (MDS-UPDRS) Part III (Motor Examination) score after 12 weeks of treatment. Evaluation time point: \geq 12 hours from the most recent dose of anti-PD drug.
- Concomitant Events and Management Strategies: Any concomitant medications (excluding the investigational product and stable anti-PD drugs at enrollment) or treatments that may affect the PD progression will be addressed using therapeutic strategies.
- Population-level Summary: Least squares mean difference in the change from baseline in MDS-UPDRS Part III (Motor Examination) scores between the TJ0113 capsule group and the placebo group after 12 weeks of treatment. Evaluation time point: \geq 12 hours from the most recent dose of anti-PD drug. (Refer to Section [6.10.1.1](#))

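### Supplementary Analysis 2 removes Part III scores after an added PD treatment but, read literally, keeps them after a levodopa reduction that the protocol permits

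*SAP*

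**What the plan says.** SAP 3.1 names one intercurrent event for the primary estimand: "Any concomitant medications (excluding the investigational product and stable anti-PD drugs at enrollment) or treatments that may affect the PD progression". Protocol 11.4.2 has the same carve-out: "excluding the investigational product and stable anti-PD medications at the time of enrollment) or treatment that could potentially impact the PD disease process". The strategy is called a therapeutic or treatment strategy, which I read as treatment policy. The table in SAP 6.10.1 confirms that the primary MMRM uses it without imputation.

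SAP 6.10.1.3 repeats the definition for Supplementary Analysis 2, "Any concomitant medications (excluding the investigational product and stable anti-PD medications at the time of enrollment) or treatments that may impact the PD progression", and switches to a hypothetical strategy, "wherein data following the concomitant event will be excluded and treated as missing data". The missing values are then multiply imputed under missing at random, by the method in Appendix 11.1.

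For background treatment, Protocol 5.1.1 says that "the original regimen of the background medication for PD should be maintained during the study". Protocol 7.2.1 makes one exception, for subjects whose background treatment includes levodopa: "if any AE such as dyskinesia occur, the dose of levodopa is allowed to be reduced at the discretion of the investigator".

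**The concern.** The carve-out is fixed at enrolment. A drug that was stable then remains an excluded drug, and lowering its dose is not naturally a new medication or a new treatment. So the one background dose change that the protocol expressly allows is not named in the estimand and does not trigger the hypothetical strategy.

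The plan itself treats levodopa as important. Stable use is the only stratification factor, a covariate in the model and a subgroup. An analysis that removes scores after PD treatment is added, but keeps them after levodopa is cut, does not answer a clear question. The trigger for a reduction is a post-randomisation adverse event, which may depend on the assigned treatment. If reductions differed between arms, the analysis meant to set treatment changes aside would still carry their effect, and the reader would have no table from which to judge it.

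**Working it through.** **Step 1. Does any other rule catch a permitted levodopa reduction?**

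| Place | What happens to scores after the reduction |
|---|---|
| Primary analysis (SAP 6.10.1.1) | Kept, by treatment policy. This is coherent. |
| Supplementary Analysis 1, PPS (SAP 5, 6.10.1.3) | Kept. The PPS removes major deviations only, and a permitted reduction is not a deviation. |
| Supplementary Analysis 2 (SAP 6.10.1.3) | Kept on the literal reading, because the drug was stable at enrolment. |
| Prohibited medications (Protocol 7.2.2) | Not caught. The rule has its own entry-based carve-out: "excluding those which have been on a stable dose for PD at the time of study entry". |
| Medication summaries (SAP 6.8) | By ATC level 2 and preferred name, plus listings. No count of dose changes by arm. |

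The adverse-event tables do not fill the gap. SAP 6.12.2 counts events leading to dose reduction, but Protocol 9.4.1.2 records that action for the investigational product.

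**Step 2. Is there a figure in the plan to reproduce?** No. The sample size has no formal basis, and the documents give no SD, no target effect, no frequency of reductions and no effect of a reduction on Part III. Only the group sizes are given: 150 / 2 = 75 per cohort, split 50 and 25, so about 50 in each of the three groups.

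**Step 3. Scale, on assumed inputs.** Let p be the share of an arm whose levodopa is reduced before week 12 and s the mean Part III shift in those subjects. The distortion of the active minus placebo difference is

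B = p(active) × s(active) − p(placebo) × s(placebo),

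or [p(active) − p(placebo)] × s when the shift is the same in both arms. All values of p, s and SD below are assumptions.

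| Reduced, active | Reduced, placebo | B at s = 1 | B at s = 3 | B at s = 6 |
|---|---|---|---|---|
| 2% | 2% | 0 | 0 | 0 |
| 5% | 2% | 0.03 | 0.09 | 0.18 |
| 10% | 2% | 0.08 | 0.24 | 0.48 |
| 10% | 10% | 0 | 0 | 0 |
| 20% | 4% | 0.16 | 0.48 | 0.96 |

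The standard error of the difference is SD × √(2/50) = 0.2 × SD. For an SD of 8, 10 or 12 it is 1.6, 2.0 or 2.4 points. The largest case is then 0.96/1.6 = 0.60 down to 0.96/2.4 = 0.40 standard errors.

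**Step 4. What happens to scores once they are set to missing?** The PROC MI programs in Appendix 11.1 use levodopa status, baseline and the four post-baseline visits. Treatment group is not among the variables. Active-arm scores would be imputed from a model pooled over arms, which can pull the difference toward zero. Earlier visit scores carry some information on treatment, so this dilution would be partial. Widening the event definition without changing the imputation model could therefore replace one distortion with another.

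**The case against.** **Timing.** Supplementary Analysis 2 concerns only the primary endpoint, scored at least 12 hours after the last anti-PD dose. A change in the current dose would show most directly at the 2 ± 1 hour assessment, which is secondary and outside this analysis. The 3 to 6 point shifts take no account of this. This objection stands: the effect may be smaller than the table suggests.

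**Population.** Entry requires Hoehn and Yahr 1 to 2.5, untreated patients are eligible, severe dyskinesia that may affect the motor examination is an exclusion, and treatment lasts 12 weeks. Only levodopa users are exposed. If half of an arm used levodopa (an assumption), 10% to 20% of the arm would mean 0.10/0.5 = 20% to 0.20/0.5 = 40% of users. The larger rates may well be high.

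**Looser reading.** One can argue that a drug whose dose is cut is no longer a stable anti-PD drug and so leaves the carve-out. A reader might infer that a dose change can never count as an event; the wording is not that settled. But the SAP does not state the looser reading, and two programmers could build different datasets.

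**Narrower target.** A hypothetical world without added therapy is a legitimate question, and whether to set aside an adverse-event-driven reduction is an estimand choice. That is right, but the SAP does not say that it made this choice.

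**Partly handled.** Protocol 7.2 and 7.3 have dose, dates and background administration recorded, and SAP 6.8 lists medications. Background changes that the protocol does not permit can be treated as deviations and so reach the PPS analysis. That leaves mainly the permitted levodopa reductions, which still have no rule and no table.

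**Conclusion.** The gap is real on the literal text and is confined to one supplementary analysis and to a missing tabulation. It should be closed before unblinding.

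Two stronger inferences are tempting and are not supported. The first is that the primary result is biased: it is not affected, because treatment policy keeps these scores by design. The second is that the drug effect is understated by a given amount. That needs more reductions on active drug and a worsening of the off-medication score after a reduction, and the documents establish neither. Dyskinesia is not named among the phase I events reported in Protocol 2.4.2 or the toxicities in 2.5.1, although phase I was in healthy subjects.

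The distortion is zero if reductions are equally frequent and have the same effect in each arm. It is likely below one standard error: on the assumed inputs, at most 0.4 to 0.6 of one. Since the study makes no formal test and reports nominal P-values, the issue is the coherence and readability of the supplementary analysis, not error control.

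**What to change.** 1. Keep treatment policy for the primary analysis.
2. In SAP 3.1 and 6.10.1.3, name a change in dose or a stop of a background anti-PD drug after the first dose of study drug as an intercurrent event, with its strategy in each analysis. Record the addition in SAP 8, which now reports no changes from the protocol.
3. In Supplementary Analysis 2, set Part III scores after this event to missing.
4. In Appendix 11.1, include treatment group in the imputation model, or impute separately by arm. Sensitivity Analysis 2 uses the same appendix, so say whether the change applies there too.
5. Tabulate these events by arm.

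The cost is SAP wording, some programming and one table. Dose, dates and background administration are already collected. The downside is more scores imputed under missing at random in one supplementary analysis, an assumption open to doubt after a reduction triggered by an adverse event. In the most extreme case above (20% against 4%), 10 + 10 + 2 = 22 of 150 subjects would be affected; with few reductions the cost is slight and the table will show it. The clinical rule that permits the reduction is not changed.
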